6.8 Premature termination of the study.....	14
7. PATIENT SAFETY.....	15
7.1 Section 10 WMO event.....	15
7.2 AEs, SAEs and SUSARs.....	15
7.3 Follow-up of adverse events.....	16
8. STATISTICAL ANALYSIS.....	17
8.1 Descriptive statistics.....	17
8.2 Primary study parameter(s).....	17

8.3 Secondary study parameter(s)	17
9. ETHICAL CONSIDERATIONS	18
9.1 Regulation statement	18
9.2 Recruitment and consent	18
9.3 Objection by minors or incapacitated subjects	18
9.4 Compensation for injury	18
9.5 Incentives	18
10. ADMINISTRATIVE ASPECTS, MONITORING AND PUBLICATION	19
10.1 Handling and storage of data and documents	19
10.2 Monitoring and Quality Assurance	19
10.3 Amendments	19
10.4 Annual progress report	19
10.5 End of study report	19
10.6 Public disclosure and publication policy	20
11. STRUCTURED RISK ANALYSIS	21
11.1 Potential issues of concern	21
11.2 Synthesis	21
12. REFERENCES	22

SUMMARY

Background: Various approaches in the preoperative setting have demonstrated a positive effect on nutritional status and reduction of complications.

Objective: To investigate whether protein-rich nutrition of *FoodforCare* in the preoperative setting improves functional outcomes within 3 weeks in surgical patients, compared to usual care.

Study design: Randomized controlled trial

Intervention and procedure: Surgical patients are screened at the preoperative out-patient clinic for risk of malnutrition by nurses. In case of a score ≥ 1 , which indicates a risk for malnutrition and a potential participant, patients are asked to participate. Participants randomized to the intervention group will receive the FoodforCare service in the preoperative setting for 3 weeks, which consists of five to six small protein and energy-rich meals. After an individual intake, the composition of the dishes will be tailored to the needs of the patient in terms of composition, diet, taste, flavor and portion size. Participants randomized to the control group will continue their usual diet in the preoperative setting for 3 weeks.

Main study parameters/endpoints: The primary outcome is the change in handgrip strength (between baseline and end of the intervention) between the 2 groups. Secondary outcomes include change in nutritional status, nutritional intake, patients' satisfaction, quality of life, length of stay and postoperative complications.

Nature and extent of the burden and risks associated with participation, benefit and group relatedness: There are no additional tests or hospital tests necessary for the patient. This study will not confer any no additional risks. Food will be delivered within the expiration dates and the meals will be prepared according to the regular hygienic and food safety criteria that are valid. Possible serious reactions to the meals will be noted as SAE's.

1. INTRODUCTION AND BACKGROUND

Each year, approximately 1.4 million patients in the Netherlands are operated.(1) Adequate nutritional intake, mainly protein intake, before surgery is important to improve preoperative muscle strength and functional capacity. However, up to 40% of patients admitted to the hospital suffer from malnutrition and this further deepened during hospitalization(2), which is an independent risk factor for peri-operative morbidity and severe complications(3), ranging from increased muscle loss, to higher infection rates, delayed wound healing and subsequently a prolonged hospital stay.(4) Recent studies also reported a higher rate of postoperative complications in patients with respectively a low muscle mass, assessed using computed tomography (CT), or muscle weakness, defined by handgrip strength, preoperatively.(5, 6) These malnutrition-related complications have a major impact on hospital resources and healthcare costs.(7)

There are various types of approaches used in the hospital setting to optimize the nutritional status and improve functional capacity of hospitalized (surgical) patients.(8, 9) In enhanced recovery programs, which aims to ameliorate the response to surgery, various nutrition-specific aspects are included such as preoperative nutrition risk screening and carbohydrate loading, early feeding of normal food and inclusion of oral nutritional supplements prior to operation and for at least the first 4 postoperative days.(10) An adequate food service is another strategy to improve protein intake and thereby the nutritional status. An innovative hospital food formula, FoodforCare, is recently developed and implemented hospital-wide in the academic hospital (Radboudumc) in Nijmegen. This formula consists of small protein-rich dishes served 6 times a day, that aims at improving appetite and contributing to patients' wellbeing. Recent publication shows that FfC improves reached protein and energy requirements, compared to the standard food service.(11) Extension of the study period to the out-of-hospital setting is recommended to explore the effects of long-term exposure to this concept on clinical outcomes.

However, research has mainly focused on approaches in the postoperative period and during hospital stay, while evidence shows that this phenomenon might also be relevant in the preoperative setting.

A recent meta-analysis shows that preoperative nutritional support with parenteral nutrition improves clinical outcomes, such as length of stay and postoperative complications, in abdominal surgical patients at nutritional risk.(12) Another study shows that meaningful changes in postoperative functional exercise can be achieved with a prehabilitation program.(13) Studies on preoperative protein-rich diets are lacking.

Since FoodforCare has proven to increase nutritional intake in the hospital setting, we aim to determine whether protein-rich nutrition of *FoodforCare* in the preoperative setting improves functional outcomes within 3 weeks in surgical patients at risk for malnutrition, compared to usual care. We expect that this diet will have a beneficial effect on protein intake and therefore, on the nutritional status of the patients. Another positive effect might result from a reduction in postoperative complications.

2. OBJECTIVES

2.1 Primary objectives:

To investigate whether protein-rich nutrition of *FoodforCare* in the preoperative setting improves functional outcomes within 3 weeks in surgical patients at risk for malnutrition, compared to usual care. The primary functional outcome is determined as the difference in handgrip strength between baseline and the end of intervention.

2.2 Secondary objectives:

To investigate whether protein-rich nutrition of *FoodforCare* in the preoperative setting improves:

1. Functional status: Short Performance Physical Battery
2. Nutritional status (weight, Patient Generated Subjective Global Assessment (PG-SGA))
3. Protein- and energy-intake relative to requirements
4. Length of stay, number of readmissions and postoperative complications
5. Quality of life
6. Satisfaction of patients regarding food quality (and service when FoodforCare)

3. STUDY DESIGN

This is a randomized controlled trial (RCT). Given the nature of the intervention it is not possible to blind participants and investigators. This study will be conducted at the Radboud University Medical Center. This study will be directed according to the principles of the World Medical Association Declaration of Helsinki (64th WMA General Assembly, October 2013).

[figure not shown]
3.1 Recruitment

Surgical patients will be screened at the preoperative out-patient clinic for risk of malnutrition with the MUST (Malnutrition Universal Screening Tool) score by nurses. In case of a score ≥ 1 , which indicates a risk for malnutrition and a potential participant, nurses will ask the participant whether they are happy to receive information about the study and will subsequently call the coordinated researcher. The researcher will conduct the initial screening and will inform the patient about the study. The patient will also be informed that participation is voluntary and withdrawal is possible at any time. The patient will receive an information leaflet with further information. A minimum of 24 hours later the researcher will contact the patient by telephone and ask whether he/she will participate in the study. After that, the informed consent form will be signed by the patient and send to the researcher, who will register the patient. The medical attending staff provided permission to approach individual patients.

3.2 Randomization and blinding

The researcher will randomize the patient by using a password-protected randomization service which is part of the clinical data management system "Research Manager". Participants are randomized to either the intervention or the control group, using block randomization, stratified for underlying disease and MUST score (MUST1 or MUST $>$ 1). After randomization, the system provides a trial participants number, who will be documented in a designated source document with the patient information. The study number and birth date will be listed on all study documents. Blinding seems not possible for the coordinating researcher, since one group will receive FoodforCare and the other group will receive no additional products. Whether blinding is possible for the researcher will be examined during the pilot study. In that case, patients will be asked not to tell the researcher in which group they are allocated. Patients have to be aware of the group allocation. Any important protocol modifications will be communicated with the Medical Ethics Committee.

Figure 1. Study design

4. STUDY POPULATION

4.1 Population

The study population consists of Dutch speaking patients undergoing surgery with a risk for malnutrition (MUST \geq 1), with oral intake, living within a radius of 40km from the Radboudumc. Patients on tube- or parenteral feeding, patients with renal insufficiency (MDRD-GFR < 60ml/min and/or proteinuria) or patients with impairment, which would prohibit the patient from full participation in the study, were excluded from the study.

4.2 Inclusion criteria

- 18 years or older
- MUST score \geq 1
- living within a 40 km radius around Nijmegen/Veghel
- inclusion at least 4 weeks before surgery
- oral intake
- surgery: Urology, Orthopedics, colorectal and oesophagus.

4.3 Exclusion criteria

- renal insufficiency (MDRD-GFR (glomerular filtration rate) < 60ml/min and/or proteinuria)*
- underlying condition which makes it impossible to perform hand grip strength

*proteinuria is defined in case of a protein creatinine ratio > 0.5g/10mmol or an albuminuria > 300mg/day.

4.4 Sample size calculation

The sample size calculation is based on the primary outcome of this study: the change in handgrip strength after 3 weeks between the groups. Based on literature and data from our previous study, patients will have a baseline handgrip strength of 28kg with a standard deviation of 5kg.(6) Assuming a difference of 2kg (7%) is a clinically relevant difference in favor of FoodforCare, we estimate that 209 patients are needed in order to obtain a power of 80% (two-tailed t-test, alpha 0.05). 251 patients should be included, assuming a drop-out rate of 20%. In order to improve the power significantly, we will make use of the ANCOVA test. By multiplying the number of patient with $(1-(\rho^2))$ a total of 228 patients will be needed. The correlation between the baseline and end of treatment (ρ) is estimated at 0.3, also because of the heterogeneity of the substantiated studies.

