6.6 Replacement of individual subjects after withdrawal

During the inclusion period, additional patients will be included to be able to achieve the necessary number of patients in case of withdrawal of patients during the study.

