8.2 Primary study parameter(s)

The primary study parameter is the change in hand grip strength between baseline and the end of the interventions, in percentages, compared to the control and the intervention group. This difference in percentages is a continue variable and will be compared by using the ANCOVA test.

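### Section 4.4 inflates for 20% drop-out by multiplying by 1.2 instead of dividing by 0.8, so the chain 209, 251, 228 needs restating; power changes by nil to about 2 points and no added enrolment is required

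*Combined protocol and SAP*

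**What the plan says.** Section 4.4 builds the enrolment target in three steps.

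- **Base.** It gives a "baseline handgrip strength of 28kg with a standard deviation of 5kg" and continues: "Assuming a difference of 2kg (7%) is a clinically relevant difference in favor of FoodforCare, we estimate that 209 patients are needed". The stated test is a two-sided t-test at alpha 0.05 with 80% power.
- **Drop-out.** "251 patients should be included, assuming a drop-out rate of 20"%.
- **ANCOVA.** It multiplies by (1 − rho²), with rho put at 0.3, and concludes that "a total of 228 patients will be needed".

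Two other sections bear on this. Section 6.6 says that "additional patients will be included to be able to achieve the necessary number of patients in case of withdrawal". Section 8.2 sets the scale of the analysis: "The primary study parameter is the change in hand grip strength between baseline and the end of the interventions, in percentages".

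**The concern.** If a fraction d of enrolled patients is lost, N completers require N/(1 − d) enrolled. Multiplying by (1 + d) always falls short, because the loss applies to the larger, enrolled number. The 251 looks like 209 plus a fifth, and the 228 is built on it.

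The starting figure is also hard to trace: a standard t-test calculation at 2 kg and SD 5 kg gives a total about ten below 209.

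Section 4.4 is the only justification of the enrolment target. If its steps are wrong, the claim of 80% power after 20% drop-out may not hold. The replacement rule in 6.6 also lacks a clear target, because 4.4 never prints the number of evaluable patients that the ANCOVA needs.

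**Working it through.** **Inputs.** From 4.4: difference 2 kg (2/28 = 7.1%, printed as 7%), SD 5 kg, two-sided alpha 0.05, power 80%, drop-out 20%, rho 0.3. Allocation is not stated (3.2 says only that block randomization is used), so 1:1 is assumed.

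**1. Reproducing the printed chain from 209.**
- 209 × 1.2 = 250.8, printed as 251.
- 1 − 0.3² = 0.91, and 251 × 0.91 = 228.4, printed as 228.

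Both later figures therefore follow from 209 with a multiplier of 1.2.

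**2. Drop-out step.**
- Completers left from 251: 251 × 0.8 = 200.8, about 201 rather than 209.
- Loss that 251 can absorb: 1 − 209/251 = 16.7%.
- Correct inflation: 209/0.8 = 261.25, so 262.

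Carried through the ANCOVA factor:
- Completers left from 228: 228 × 0.8 = 182.4, about 182.
- Completers implied by the plan's own base: 209 × 0.91 = 190.2, about 190.
- Enrolment for that: 190.19/0.8 = 237.7, so 238.

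**3. The base of 209.** Two-sided two-sample t-test, noncentral t, arms as equal as possible; smallest total N reaching 80%:

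| Difference | SD | Total N | Power at that N |
|---|---|---|---|
| 2 kg | 5 kg | 199 (200 with equal arms) | 80.2% (198 gives 79.97%) |
| 1.96 kg (7% of 28 kg) | 5 kg | 207 | 80.1% |
| 1.95 kg | 5 kg | 209 | 80.1% |
| 2 kg | 5.13 kg | 209 | 80.1% |

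One-sided testing (156), 90% power (266) and 2:1 allocation (223) do not give 209. Exactly 2 kg and 5 kg do not give it either. But 1.95 kg rounds to 2 kg (1.95/28 = 7.0%) and 5.13 kg rounds to 5 kg, so 209 is compatible with the inputs as printed.

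**4. Correct chain from exactly 2 kg and SD 5 kg.** 200 × 0.91 = 182 evaluable; 182/0.8 = 227.5, so 228 enrolled. The higher base and the short inflation offset each other, and the printed final number is recovered.

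**5. Power after 20% drop-out.** ANCOVA in kg, residual SD = SD × √0.91, N − 3 degrees of freedom:

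| Inputs | 182 completers | 190 completers |
|---|---|---|
| 2 kg, SD 5 kg | 80.3% | 82.0% |
| 1.96 kg, SD 5 kg | 78.7% | 80.4% |
| 1.95 kg, SD 5 kg | 78.3% | 80.0% |

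The smallest ANCOVA N for 80% is 181 at 2 kg, so 228 tolerates a loss of 1 − 181/228 = 20.6%. At 1.95 kg it is 190, so 228 tolerates 1 − 190/228 = 16.7%.

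**6. Sensitivity to rho.** At 2 kg, SD 5 kg and 182 completers, power is 78.2% for rho 0.2 and 83.4% for rho 0.4.

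**The case against.** The strongest reply is that nothing in the trial has to change. Correct arithmetic from the printed 2 kg and 5 kg leads to 228, and the worst case is about 2 points of power under inputs that are not printed. The guess at rho moves power more than the drop-out slip does. Section 6.6 also allows extra patients after withdrawals, so the inflation factor is not the only protection. All of this stands, and it limits the point to restating the figures. It does not make the drop-out step right: 209, 251 and 20% stand in adjacent sentences and disagree without any outside assumption. Nor does 6.6 repair it, because no evaluable ANCOVA number is printed for the rule to aim at.

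A second reply is that 209 is not an error. The inputs are rounded and are attributed to literature and the group's own previous data. This also stands. A reader might infer from the recomputed 199 or 200 that 209 is an arithmetic mistake. The documents do not show that: 209 is within the rounding of the printed difference and SD, and it errs on the larger side. What is missing is the unrounded input.

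Third, the power figures are for an analysis in kg, while 8.2 analyses percentage change. That is a fair limit on their precision. It does not touch the drop-out arithmetic.

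**Conclusion.** The drop-out inflation in 4.4 is wrong as written. On the plan's own base, 251 should be 262, and 228 leaves about 182 completers where 190 are implied (238 enrolled). The base of 209 cannot be traced to exactly 2 kg and SD 5 kg but is compatible with their rounding, so it is under-reported rather than shown to be wrong.

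A reader might infer that the trial is underpowered or must recruit 238 or more. The documents do not support that. At exactly 2 kg and SD 5 kg, 228 enrolled meets the 80% target after a 20% loss (80.3%). If 209 is the intended base, power is about 78.3%, which is 1.7 points below the 80% target. Only the sponsor can say which inputs were used.

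The arithmetic on 209, 251 and 228 rests on no assumption. The power figures assume 1:1 allocation, rho 0.3 and an ANCOVA in kg.

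**What to change.** In section 4.4:

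- State the exact difference and SD used, and that the calculation is in kg.
- Apply (1 − rho²), then divide by 0.8, and print both the evaluable and the enrolled number.
- If exactly 2 kg and SD 5 kg are meant, replace the chain with 200, then 182 evaluable, then 228 enrolled (80.3% power for an ANCOVA in kg with rho 0.3), and delete 209 and 251.
- If 209 is the intended base, delete 251, keep 228 and restate its power after 20% drop-out as about 78% (78.3% with 182 completers), not 80%.

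In section 6.6, cite the evaluable number from 4.4 as the target of the replacement rule.

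The cost is two or three corrected sentences in 4.4 and one cross-reference in 6.6. No patients need to be added.

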5. INTERVENTION

5.1 Name and description of investigational products

The FoodforCare at Home concept consists of five to six small protein and energy enriched meals that will be delivered twice a week. After an individual intake, the composition of the dishes will be tailored to the needs of the patient in terms of composition, diet, taste, flavor and portion size. Besides the meals, patients in the intervention group will also receive an information leaflet about the importance of protein during treatment and how to reach their protein requirements. The control group has no restrictions to their diet. The dishes are prepared by caterer Maison van den Boer, meeting the highest standards of nutrition and quality and served according to the regular hygienic and food safety criteria that are valid, and delivered twice a week by FoodforCare.

5.2 Summary of findings from clinical studies

Uit recente literatuur komt naar voren dat adequate preoperatieve voedingsondersteuning resulteert in betere klinische resultaten. Een recente meta-analyse uit 2015, bestaande uit gerandomiseerde, gecontroleerde trials, heeft gekeken naar het effect van preoperatieve voedingsondersteuning op klinische uitkomsten in ondervoede patiënten(14) Het betrof voornamelijk gastrointestinale chirurgie met parenterale therapie. Er werd geconcludeerd dat de ondersteuning superieur was voor wat betreft het verbeteren van klinische uitkomsten, onder andere in het verminderen van postoperatieve complicaties en verminderen van de opnameduur.

Een andere studie uit 2012 toonde aan dat preoperatieve voedingsupport (minimaal 7 dagen parenterale of enterale voeding) bij abdominale chirurgische patiënten met een verhoogd risico op ondervoeding (NRS 5 of hoger), leidde tot een significante vermindering in complicaties en opnameduur, ten opzichte van de controle groep.(15)

Daarnaast wordt er in het ERAS (enhanced recovery after surgery) protocol onder andere beschreven op welke manier uitkomsten na chirurgische ingreep kunnen worden verbeterd. Hierbij wordt gestreefd naar minimale stress rondom de operatie. Koolhydraat drankjes preoperatief lijken hierbij effectief in het verminderen van postoperatieve insuline resistentie.(9, 10)

5.3 Summary of known and potential risks and benefits

The food products of Maison van den Boer meet the highest standards of nutrition and quality and has therefore, no additional risk compared to usual products. All products will be served according to the regular hygienic and food safety criteria that are valid. Possible serious reactions to the products will be noted as SAE's. There are no additional tests or hospital visits necessary for the patient. Therefore, we do not expect any potential risk.

5.4 Dosages, dosage modifications and method of administration

The composition of the dishes are developed to enable maintenance and if possible improvement of the nutritional status of the patient. The aim is, therefore, to stimulate protein intake as much as possible with a protein intake of at least 1.2 gram per kilogram bodyweight per day. On average, this is equivalent to an intake of 90-95 grams of protein per person per day (assuming an average weight of 75-80 kg). Protein intake of 20-25 grams per meal would ensure optimal postprandial protein synthesis in the muscles.(14) This and other

information about the protein content of the FoodforCare products will be spread to the patients in order for them to make decisions that contribute to their protein requirements.

6. METHODS

6.1 Primary outcome

The primary outcome is the change in handgrip strength (between baseline and end of treatment) between patients receiving FoodforCare and patient on usual care (table 1).

Handgrip strength (HGS) is a valid non-invasive method to measure muscle functionality and serves as a predictor for the overall muscle strength, nutritional status and change in nutritional status of patients.(15) Importantly, studies have shown that impaired handgrip strength may be an indicator of increased mortality and morbidity, such as increased postoperative complications, length of stay, readmissions, and decreased physical status.(6, 16) HGS will be measured with the JAMAR meter on a standardized manner for the researcher.(17) Whether blinding is possible for the researcher will be examined during the pilot study.

6.2 Secondary outcomes

- Functional status: besides HGS, change in functional status will be evaluated with the Short Physical Performance Battery.
- Nutritional status: change in nutritional status will be assessed with the PG-SGA and measurements of body weight (table 1).(18) PG-SGA will be filled in by the patient and a member of the research team. Body weight will be measured on a calibrated weighting scale (type ..) in sober state. Relative weight changes will be presented as the percent weight change relative to the weight at baseline. Body Mass Index will be calculated.
- Nutritional intake: difference in nutritional intake (protein and energy) will be evaluated at every time point based on a 2-day food diary filled in by the patient. The food diary will be cross checked by a member of the research team and, if necessary, the patient will be called for clarification. The food items will be coded and calculated according to the Dutch Food Composition Table (NEVO, RIVM). During the pilot study, we will evaluate if a "symptom diary" should be assessed.
- Length of hospital stay and readmission: reported from the medical record of the patients.
- Postoperative complications: reported from the medical record of the patients and classified using the Clavien-Dindo classification.(19) Grade of severity is based on the type of treatment for the specific complication. Infectious complications will be reported based on the definition of the American College of Chest Physicians/Society of Critical Care Medicine Consensus Conference.(20)
- Quality of life: change of quality of life will we assessed with the SF-36 questionnaire filled in by the patients. The Caregiver Reaction Assessment will be filled in by their caregiver.(21)
- Patient satisfaction:
 - o Both groups will fill in a questionnaire with questions about their wellbeing and stress level regarding shopping and cooking of their meals.
 - o In the intervention group, the Net Promoter Score (NPS) with additional questions will be used to assess patient satisfaction in the intervention group at time point 3. The NPS is determined by asking the question: 'How likely is it

that you would recommend FoodforCare to a friend or colleague?'. The score ranges from 1-10 and patients can be grouped in 'promoters' (9-10 grading), 'passively satisfied' (7-8 grading) and 'criticasters' (0-6 grading). The NPS is finally calculated by subtracting the percentage of criticasters from the percentage of promoters.(22) Additional questions about satisfaction with respect to the food supply and logistics of FoodforCare will be answered by the patients to explain their score.

Both questionnaires are self-composed and based on validated questionnaires because there is no Dutch validated questionnaire available about a home-delivered meal service.

